## 4.2 Drug Accountability

Each UCSF campus investigator using Schedule I substances in research must obtain their own Schedule I registration with the DEA and is responsible for the ordering, security, accountability and disposition of all product ordered under their registration. Psilocybin will be obtained from the laboratory of [name] at Johns Hopkins University, and the drug will be shipped to the Investigational Drug Service of the Department of Pharmaceutical Services at UCSF Medical Center ([name]; [contact]). The pharmacy has been used for the storage and preparation of Schedule I controlled substances for individual campus Schedule I registrants for many years.

**Storage:** Schedule I substances will be stored in one of two large combination lock safes located in the investigational drug storage room of the UCSF Inpatient Pharmacy. The investigational drug storage room is a limited access storage room located in the basement of Moffitt Hospital on the UCSF Parnassus Campus ([name]). The room bears a security lock, accessible to the investigational pharmacy staff. The combination of the safe is known only to the investigational drug pharmacy staff.

Upon receipt of a medication order from the investigator, the drug supply will be accessed by the investigational pharmacy staff. The ordered dose will be obtained, placed in appropriate pharmacy dispensing container and labeled for the research subject. The dose contained will be sealed with a tamper evident seal. Research staff will escort the patient to the Inpatient Pharmacy on the day of dosing. Drug will be dispensed directly to the research subject by the pharmacy staff after confirming patient identification and acquiring the patient's signature on the pharmacy's chain of custody documentation. The subject will then be escorted by study staff from the Inpatient Pharmacy through indoor hallways that connect the Moffitt Hospital (where the pharmacy is located) to the Langlely Porter Psychiatric Institute (where the drug administration will take place).

**Dispensing:** Psilocybin was shipped from [name] in powder form and will need to be allocated into gelcaps by the UCSF Investigational Drug Service. Subjects will be dispensed one gelcap with their dose based on weight, as measured prior to the drug treatment day by study staff. Psilocybin will be ingested by study subjects in the testing area (Room A-310) of the third floor annex of Langlely Porter Psychiatric Institute.

**Records:** Record keeping will be in accordance with federal and state regulations for Schedule I controlled substances. Inventory will be taken at least every two years at end of the business day and maintained in a printed form.

### **4.3 Drug Ordering**

UCSF has obtained psilocybin directly from [name] at Johns Hopkins University.

### **4.4 Packaging and Labeling of Study Drugs**

Drugs will be packaged and labeled per UCSF institutional standards, adhering to applicable local and federal laws.

## 5 Treatment Plan

### 5.1 Dosage and Administration

Treatment will be administered on an outpatient basis.

**Table 5.1 Regimen Description**

Study Drug	Premedication / precautions	Dose	Route	Schedule
Psilocybin	Avoid all other psychotropic agents within 48hr of each dose	0.3mg/kg or 0.36mg/kg (moderate-to-high)	Oral	After 4 group therapy visits

Psilocybin is not physiologically toxic at the doses being used in this study. No human data exists that suggest what a toxic dose of psilocybin might be, but experiments in animals suggest that the LD50 of psilocybin in humans may be in the range of grams [91], which is two orders of magnitude higher than the highest dose to be used in this study. Patients could have short-term (<24hr) challenging psychological reactions. Patients who have a serious adverse event consisting of a negative psychological reaction lasting >24hr will be followed by a study physician until the resolution of the event and, at the discretion of the PI, may be removed from the study. There is reason to believe that participating in the integration group therapy sessions after a negative psychological reaction may help in recovering from such an event, and so participants will not automatically be removed from the study merely for having a prolonged negative psychological reaction to the psilocybin session (See Section 7.3 for definitions of Adverse Event.)

#### 5.1.1 Other Modalities

Patients will participate in group therapy sessions following a modified manual of Brief Supportive-Expressive Group Therapy (SEGT) [76]. SEGT emphasizes therapeutic goals that include enhancing mutual support, openness and emotional expression, improved social and family support, and detoxifying death and dying. The weekly sessions will last 90 minutes and be conducted by 2 co-facilitators with experience leading psychotherapy groups.

### 5.2 Monitoring and Toxicity Management

Of the hundreds of subjects administered psilocybin in clinical or research settings over the last two decades, none have required emergent psychiatric medications or emergency department care [24, 143, 154]. Each subject receiving psilocybin will be evaluable for safety. The safety parameters include physical findings and spontaneous reports of adverse events reported to the investigator by subjects and primary caregivers. Each subject will be assessed periodically for the development of any toxicity as outlined in [Section 6 Study Procedures and Observations](#). Toxicity will be assessed according to the NIH Division of AIDS Table of Grading of Severity of Adult and Pediatric Adverse Events V2.0 ([http://rsc.tech-res.com/Document/safetyandpharmacovigilance/DAIDS\\_AE\\_Grading\\_Table\\_v2\\_NOV2014.pdf](http://rsc.tech-res.com/Document/safetyandpharmacovigilance/DAIDS_AE_Grading_Table_v2_NOV2014.pdf))

. We will monitor specifically for hypertension, hypotension, tachycardia, nausea, emesis, headache, anxiety, dysphoria, mania, suicidality and psychosis during drug sessions using the Adverse Event Medication Session Rating Form (see Appendix). Acute physical adverse events (e.g., nausea or hypertension) will trigger increased frequency of monitoring. Acute psychological adverse events will be managed by supportive reassurance and, if needed, medications such as lorazepam or olanzapine. Further management of physical or psychiatric adverse events will depend upon the judgment of the on-call study physician and may include, if necessary, transportation to the UCSF Parnassus Emergency Department, which is located immediately adjacent to the Langley Porter Psychiatric Institute.

## 6 Study Procedures and Observations

**See Appendix A for a timeline of all assessments**

### 6.1 Study Site

All in-person pre-treatment and treatment patient contact will occur at the Langley Porter Psychiatric Institute (LPPI) at [name]. LPPI is a psychiatric hospital within the UCSF Medical Center Parnassus Campus and is immediately adjacent to the UCSF Parnassus Emergency Department.

### 6.2 Selection of Measures

Antiretroviral Medication Adherence Scale (AMAS)—A single item 11-point Likert scale (0%-100%) of ART medication adherence percentage over the past week. This scale was invented for this study.

Alcohol Use Disorders Identification Test (AUDIT) – A 10-item screening tool developed by the World Health Organization to assess alcohol consumption, drinking behaviors, and alcohol-related problems.

Center for Epidemiologic Studies Depression Scale-Revised (CES-D-R)—A 20-item validated 5-point Likert scale self-report scale for the detection of depression [155] that has been shown to be sensitive to change in symptoms in palliative care patients. [156].

Client Satisfaction Scale (CSS)—A 4-item 10-point Likert scale (“very dissatisfied” to “very satisfied”) designed for this study assessing satisfaction with the intervention.

Clinical Global Impressions scale (CGI)—A widely-used 3-item clinician-administered assessment developed by the NIMH to assess change in patients in psychopharmacology trials[157].

Challenging Experiences Questionnaire (ChEQ)—A validated 26-item 6-point Likert scale of the extent to which subjects experienced challenging experiences during a psychedelic drug treatment session[158]. The scale has 7 factors: fear, grief, physical distress, insanity, isolation, death and paranoia.

Columbia Suicide Severity Rating Scale (C-SSRS)—A validated 17-item scale that assesses suicidal ideation and behavior ([www.cssrs.columbia.edu](http://www.cssrs.columbia.edu)) according to the Columbia Classification Algorithm for Suicide Assessment (C-CASA), which the FDA Division of Psychiatric Products requires be used in clinical trials it oversees.

Community Observer Rating Form (CORF)—A 13-item 10-point Likert scale developed by Griffiths et al to triangulate behavioral observations of individuals administered psilocybin [17].

Concomitant Therapeutics Checklist (CTC)—A checklist designed for this study to assess the following categories of mental health therapies used over the last week: Prescription medications, non-prescription medications, psychotherapy, mutual aid groups, self-help

techniques, integrative medicine modalities, other.

Credibility/Expectancy Questionnaire (CrEQ)—A 6-item self-report measure of cognitive and affective assessments of a mental health therapy with high internal consistency and good test-retest reliability [159] that we have adapted for psychological distress.

Demoralization Scale-II (DS-II)—An abbreviated, 16-item and 3-point version of the well-validated original 24-item Demoralization Scale [160], which is the most widely used self-report measure of demoralization in palliative care patients [29]. The DS-II has two subscales: Meaning and Purpose, and Distress and Coping Ability, and shows both good internal and external validity in palliative care patients [27, 161].

Drug Use Disorders Identification Test (DUDIT) – An 11-item screening tool developed as a parallel to the AUDIT to assess drug consumption, drug use behaviors, and drug-related problems.

Duke UNC Functional Social Support Questionnaire-5 (DUFSS-5)—A 5-item, 3-point Likert, self-report measure of perceived functional social support. The abbreviated 5-item scale has been validated in patients with severe medical illness (advanced cancer or AIDS) [162].

Experiences in Close Relationships scale—Modified 16 (ECR-M16)—A 16-item, 7-point Likert self-report measure of attachment security. The abbreviated 16-item version is reliable and has been validated in patients with severe medical illness (metastatic cancer)[163].

Group Questionnaire (GQ)—A validated self-report 30-item 7-point Likert questionnaire of therapeutic relationships in group therapy [130]. GQ has a three-factor model of group cohesion: Positive Bonding, Positive Working, Negative Relationships, all of which manifest in both member-member and member-leader relationships [164]. GQ was empirically-derived from measures in the AGPA CORE-R Battery [136] that assess therapeutic alliance and cohesion—the two factors known to best predict clinical outcomes of group psychotherapy trials [129].

Group Psychotherapy Intervention Rating Scale (GPIRS)—An empirically-derived observer-rated 48-item instrument that assesses group therapist behaviors that help create and maintain group cohesion [165].

HIV and Abuse Related Shame Inventory (HARSI)—A validated 22-item 5-point Likert scale (“Not at All” to “Very Much”) (Neufeld et al 2012, AIDS Behavior, 16:1063-1074).

Hill Interaction Matrix (HIM)—The gold standard in group therapy process measures [166], the HIM is an observer-rated instrument that assesses group therapy sessions using a 4x4 matrix of style categories (conventional, assertive, speculative and confrontational) and content categories (general, group, personal, relationship). The HIM has been used since the 1960s and there exists an extensive database of normative data against which to compare outcomes [131].

International Personality Item Pool-Openness to Experience-20 (IPIP-OE-20)—A 20-item self-report measure that uses items in the public domain to evaluate a construct approximately equivalent to Openness, which is evaluated by the NEO-PI-R [167].

Inventory of Complicated Grief (ICG)—A well-validated 19-item 5-point Likert scale (“never” to “always”) that is the gold standard self-report instrument for measuring complicated grief [168, 169].

McGill Quality of Life Questionnaire-Revised-Short (MQoL-RS)—A well-validated 15-item 11-point Likert scale that assess quality of life in palliative care patients by assessing the following

domains: Overall quality of life, Physical well-being, Psychological well-being, Social support and Existential well-being. We will only use 4 items, which are Parts A (Overall quality of life) and B (Physical symptoms).

Multidimensional Assessment of Interoceptive Awareness-Revised (MAIA-R)—A well-validated 32-item 6-point Likert scale of bodily and mental awareness that measures the following 8 domains: Noticing, Not-distracting, Not-worrying, Attention regulation, Emotional awareness, Self-regulation, Body listening and Trusting [170]. In this study, we will use the Emotional awareness (5-items), Self-regulation (4-items) and Trusting (3-items) subscales.

Mystical Experience Questionnaire-30 (MEQ-30)—A well-validated 30-item 6-point Likert scale (“none; not at all” to “extreme [more than any other time in my life]”) self-report measure of mystical-type experiences [124], derived from the earlier work of Pahnke et al. [119].

Nature Relatedness Scale, Short-Form Version (NR-6)—A 6-item version of a well-validated 5-point Likert scale self-report measure of environmental connectedness (Nisbet, E. K., & Zelenski, J. M. (2013). The NR-6: a new brief measure of nature relatedness. *Frontiers in Psychology*, 4, 11. doi:10.3389/fpsyg.2013.00813)

Palliative Performance Scale version 2 (PPSv2)—A validated clinician-administered tool based on the Karnofsky Performance Scale but adapted for a palliative care population [113, 171].

Persisting Effects Questionnaire—Spirituality (PEQ-S)—An instrument developed by Griffiths et al for subjects who have been administered psilocybin to assess enduring changes in attitudes about life, attitudes about self, mood changes, relationships, behavioral changes, and spirituality [138]. The measure also includes 4 questions about the drug experience itself concerning personal meaningfulness, spiritual significance, how psychologically challenging it was, and personal psychological insights gained. We will only use the Spirituality subscale (59-item, 6 point Likert scale [“none; not at all” to “extreme”]), and the four questions about the psilocybin experience.

Post-traumatic Growth Inventory-Short Form (PTGI-SF)—A validated 10-item 6-point Likert scale meant to assess the following psychological factors in populations that have suffered a traumatic event or major crisis: quality of relationships with others, openness to new possibilities, personal strengths, spiritual change, and appreciation of life [172].

PTSD Checklist (PCL-5): A validated 20-item, 5-point Likert scale (from “Not at All” to “Extremely”) to measure symptom criteria for PTSD from the DSM-5. [Weathers, F.W., Litz, B.T., Keane, T.M., Palmieri, P.A., Marx, B.P., & Schnurr, P.P. (2013). The PTSD Checklist for DSM-5 (PCL-5)]

Quality of Life in Life Threatening Illness Family Caregiver version 2 (QoLLTI-Fv2)—A validated 17-item 11-point Likert scale (0-10) self-report measure that assesses seven domains of quality of life in caregivers for patients with life-threatening illness: state of carer, patient well-being, quality of care, outlook, environment, finances and relationships. This instrument was developed by the same laboratory that developed the McGill Quality of Life scale [173].

Schedule of Attitudes towards Hastened Death (SAHD)—A 20-item True/False self-report measure of the desire for hastened death validated in patients with HIV/AIDS and other palliative care conditions [174].

Social Connectedness Scale-Revised (SCS-R)—A well-validated 8-item 6-point Likert scale (negatively-worded items rated from “strongly agree” to “strongly disagree”) self-report measure which has shown strong construct, convergent and discriminant validity as well as reliability ( $\alpha >$

.92) for assessing the degree to which subjects feel connected to their social environment (Lee, R. M., & Robbins, S. B. (1995). Measuring Belongingness: The Social Connectedness and Social Assurance Scales. *Journal of Counseling Psychology*, 42(2), 232-241. doi:10.1037//0022-0167.42.2.232)

State-Trait Anxiety Inventory (STAI)—A 40-item 4-point Likert scale that is the gold standard in self-report measures for state and trait anxiety [175, 176].

Supportive-Expressive Group Therapy Topic Grid (SEGT-TG)—A measure developed by Spiegel and Spira for the original studies of SEGT[75]. Independent raters watch video of therapy sessions and document the number of minutes in which particular target discussion topics are handled in the session.

Structured Clinical Interview for DSM-5 (SCID-5)—The gold standard structured clinical interview for DSM-5 criteria for major psychopathology. We will use portions of the SCID to screen for lifetime Depressive, Psychotic, Bipolar and Hallucinogen-related disorders.

Structured Clinical Interview for DSM-5 Personality Disorders (SCID-5-PD)—A self-report questionnaire based on DSM-5 criteria for personality disorders. We will use this to screen for Cluster B personality disorders.

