### Secondary

1. The difference in pre- and post-treatment mean scores of demoralization, complicated grief, depression, PTSD, shame, anxiety, quality of life, functional social support, post-traumatic growth, openness to experience, attachment security, mindfulness, global clinical impressions and ART medication adherence will trend toward significant improvement. These improvements will be sustained at 3-month follow-up.
2. The difference in pre- and post-psilocybin rates of change of group cohesion and group process will trend toward significant improvement.
3. Qualitative analyses of subject behavior and caregiver/important other reports will lead to greater understanding of the interpersonal mechanisms of action of psilocybin-assisted psychotherapy.

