## 6.4.3 Baseline Assessments (Week 1)

### 6.4.3.1 Baseline Subject Assessments

Baseline assessments will be filled out during an individual therapy session wherein the subject will meet one or both of the group therapists in the week prior to the first group therapy session. Separately, the subject's caregiver/important other will be invited to meet with study staff for a brief interview on their relationship with the subject [see Appendix C for interview guides]. The individual session for the study subject is meant to build trust and rapport with the group therapists, to learn more about the subject's life history and struggles with his health, to elicit the subject's preferences and intentions for the treatment sessions, and to orient the subject further to the intervention protocol. If screening/enrollment measures were completed within 1 week of the baseline assessment, those measures will not need to be repeated.

- AMAS, AUDIT, CESD-R, CTC, DS-II, DUDIT, DUFSS-5, ECR-M16, ICG, IOS, IPIP-OE-20, MAIA-R, MQoL- RS, NR-6, PCL-5, PTGI-SF, SAHD, SCS-R, and STAI. A clinical rater will perform a CGI and C-SSRS(Interval) for each subject.

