### **6.4.4.3 Group Therapy Sessions #5-10 (Weeks 6-8)**

Patients will undergo six group therapy sessions each 90-minutes long. Video footage of a random sampling of sessions will be analyzed with the HIM, SEGT-TG, IGMIPS and the GPIRS. Prior to each session, patients will be screened for adverse events and evaluated with the CSSR-S. Prior to sessions 5, 7 and 9, participants will fill out the CTC. After sessions 6, 8 and 10, participants will fill out the GQ. At the end of session 5, participants will fill out these questionnaires: CESD-R, DS-II, ICG, PCL-5, HARSI. After sessions 7 and 10, participants will fill out the DS-II and ICG.

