## **6.4.5 Endpoint Assessments**

### **6.4.5.1 Endpoint (Week 8) Study Measures for Subjects**

Immediately after the last group therapy session (Week 8), patients will complete the AMAS, CESD-R, DS-II, DUFSS-5, ECR-M16, ICG, IOS, MQoL-RS, NR-6, PCL-5 SAHD, SCS-R, STAI, PTGI-SF, IPIP-OE-20, MAIA-R, HARSI, CTC, and CSS. A clinical rater will perform a MoCA and CGI for each subject.

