## **6.4.6 Post-treatment/Follow Up Assessments**

### **6.4.6.1 Focus Group (Week 10)**

Two weeks after the last group therapy session, subjects and their caregivers/important others will be invited to participate in a focus group wherein they will be asked to give feedback regarding their experiences in the study. Effort will be made to get both responders and non-responders to attend the focus groups. A clinical rater will administer the C-SSRS(Interval) to each subject. Prior to the focus group each participant will fill out the DS-II and ICG. This will be video-recorded for subsequent qualitative analysis. See Appendix C for focus group guide.

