### **6.4.6.2 3-Month Follow-up for Subjects**

At 3 Months, patients will be mailed a packet with the following measures to be completed: AMAS, AUDIT, CESD-R, DS-II, DUDIT, DUFSS-5, ECR-M16, HARSI, ICG, MQoL-RS, NR-6, PCL-5, SAHD, SCS-R, STAI, PTGI-SF, IPIP-OE-20, MAIA-R, CTC, and the CSS. They will be called and encouraged to complete the packet.

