### 8.4.1 Analysis Population

All patients who enroll in the study will be included in analyses of safety and tolerability.

All patients who make any contact at all with the study (including those who are screened out over the phone) will be included in analyses of feasibility.

All patients who enroll in the trial will be included in analyses of efficacy. Repeated efficacy measures will be gathered and trended, regardless of missing data or protocol non-adherence.

All patients who participate in at least one group therapy session will be included in analyses of psychotherapeutic process.

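### The 3-month concomitant-therapy checklist looks back one week out of about 13, so other mental-health treatment that began and ended earlier in follow-up is not recorded

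*Combined protocol and SAP*

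**What the plan says.** Section 6.2 describes the CTC as a study-specific checklist "to assess the following categories of mental health therapies used over the last week". Its categories run from prescribed and over-the-counter drugs to psychotherapy, mutual-aid groups and self-help.

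The text schedules it as follows:
- Baseline, Section 6.4.3.1: it is in the list "AMAS, AUDIT, CESD-R, CTC, DS-II, DUDIT, DUFSS-5" and the measures that follow.
- Treatment, Section 6.4.4.3: "Prior to sessions 5, 7 and 9, participants will fill out the CTC".
- Week 8 endpoint, Section 6.4.5.1: the list ends with "HARSI, CTC, and CSS".
- Two-week focus group, Section 6.4.6.1: "Prior to the focus group each participant will fill out the DS-II and ICG"; the CTC is not named.
- Three months, Section 6.4.6.2: "At 3 Months, patients will be mailed a packet with the following measures to be completed", and the CTC is in that list.

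The secondary hypotheses in Section 1.4 say of the expected gains: "These improvements will be sustained at 3-month follow-up". On the efficacy data, Section 8.4.1 says: "Repeated efficacy measures will be gathered and trended, regardless of missing data or protocol non-adherence". Section 8.5.1 describes change from pre-treatment to post-treatment to 3 months. Nothing in Section 8 names the CTC.

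**The concern.** The trial has one arm. If scores hold up at 3 months, treatment taken up after Week 8 is an obvious rival explanation, and the CTC is the only structured record of such treatment that the text places in follow-up. A one-week look-back was carried unchanged from the treatment period, where forms are frequent, to a follow-up of about three months, where there is a single form.

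The gap matters most for treatment the protocol leaves open. Section 6.7 prohibits several medication classes while men are enrolled. It does not list psychotherapy, mutual aid or self-help, and it allows some drugs conditionally. Section 1.1 itself describes peer support groups forming in this community and reports that depression and anxiety improve in support groups for older people with HIV. Without a fuller record, a reader of the 3-month results cannot tell how many men had other help between Week 8 and Month 3. That information is hard to recover later.

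**Working it through.** The plan states no coverage figure, so there is none to reproduce. The inputs are a 7-day look-back (Section 6.2), one CTC after Week 8 (Section 6.4.6.2), follow-up of 3 months after treatment (Section 3.5), taken as 13 weeks, and a visit window of 7 days either way (Section 6.4), which gives 12 to 14 weeks.

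**Step 1, share of follow-up observed.** Look-back divided by follow-up length: 1/13 = 7.7%. Range: 1/14 = 7.1% to 1/12 = 8.3%.

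**Step 2, chance that an episode is caught.** Let an episode last d weeks and start at a time uniform over F weeks. The uniform start is an assumption; the documents give no pattern of uptake. The episode touches the last week if it starts later than F − 1 − d, so the probability is min(1, (d + 1)/F).

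| Episode length | F = 12 | F = 13 | F = 14 |
|---|---|---|---|
| 1 week | 2/12 = 17% | 2/13 = 15% | 2/14 = 14% |
| 4 weeks | 5/12 = 42% | 5/13 = 38% | 5/14 = 36% |
| 8 weeks | 9/12 = 75% | 9/13 = 69% | 9/14 = 64% |
| 12 weeks | 100% | 13/13 = 100% | 13/14 = 93% |

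Short courses are mostly missed and long ones mostly caught. These figures also assume that the mailed form comes back.

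**Step 3, what the two forms show together.** For each checklist category, compare Week 8 with 3 months:
- Absent, then present: new treatment, still in use. Identified, but undated.
- Present, then present: continuing. A change within the category is not visible.
- Present, then absent: stopped.
- Absent, then absent: either no treatment, or treatment begun and finished in between. The forms cannot tell these apart.

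The last cell is the main loss. Missing dates and durations are the second.

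**Step 4, which treatments are affected.** Exclusion criterion 4 (Section 3.3.2), the footnote in Section 3.4 on men who taper off medication, and Section 6.7 all restrict the main psychotropic classes during the study. Whether that period includes follow-up is not stated outright. Psychotherapy, mutual aid and self-help are outside the restriction either way.

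**Step 5, schedule consistency.** The CTC row in Appendix A appears to add enrollment, sessions 1 and 3 and the drug session, and shows no legible follow-up mark. Its column alignment cannot be read reliably, so this is a request to reconcile the row with the text, not a finding of error.

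**The case against.** A reader might infer that sustained scores cannot be separated at all from newly started treatment. The documents do not support that. The CTC is given at Week 8 and again at 3 months, so a category that is absent on the first form and present on the second already marks new, ongoing treatment. A long course, which is the kind most likely to support a score at 3 months, is the kind most likely to be recorded.

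A reader might also infer a sizeable bias in the 3-month mean. The documents say nothing about how many men start treatment or how much it helps. Any shift computed from assumed values would also count treatment that the form does capture, so no size in standard deviations can be attached to this gap.

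Other arguments against the point have force. The medication restrictions narrow the problem. Qualitative interviews (Section 6.4.6.4), the focus group and an adverse-event screen that Appendix A appears to carry into follow-up could each reveal new treatment, although none is a systematic record. Using all data whatever else men receive, as Section 8.4.1 does, is a legitimate treatment-policy approach. Efficacy is exploratory and described with summary statistics, and one arm cannot attribute durability to the intervention even with a complete treatment log.

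These arguments lower the importance of the point. They do not fill the absent-then-absent cell, and they do not supply dates.

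**Conclusion.** The point stands as a minor, inexpensive improvement. The 3-month CTC observes about 1 of 13 follow-up weeks (7.7%, range 7.1% to 8.3%). Treatment completed before that week is unrecorded, and ongoing treatment can be recognised as new only by category and without a start date. The capture probabilities rest on assumed uniform start times and on returned forms; the coverage figure rests only on the schedule and on taking 3 months as 13 weeks. The consequence is limited to interpreting the exploratory hypothesis of sustained improvement. The primary safety and feasibility objective does not depend on it. The absence of a CTC analysis in Section 8 would by itself be a missing detail; it matters here because the follow-up form needs both a longer window and a stated use.

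**What to change.** 1. In the 3-month packet, change the CTC reference period to the time since the last group session, and ask for start and stop dates. The new window then begins where the Week 8 form ends.
2. In Section 8.5.1, keep the all-patient 3-month change in DS-II and ICG as the main summary. Add the number of men who started or changed a mental-health treatment after Week 8, and show the change separately for men with and without such treatment, labelled as supportive.
3. State there that leaving out men who started treatment may overstate durability, because they may be the men who relapsed.
4. Reconcile the CTC time points in Sections 6.4.3.1, 6.4.4.3, 6.4.5.1 and 6.4.6.2 with Appendix A.

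The cost is a reworded checklist in a packet that is already mailed, plus a few summary rows. No visit or instrument is added. The downside is a longer recall period, with somewhat less exact answers, and subgroups that are small and self-selected.
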